
Page 32: Subject Exclusion Criteria
 
21. Is a study site employee or staff.
 
 • Site employees or staff include the PIs and Sub-Investigators or staff who are supervised by the PI or Sub-Investigators. 	
Page 37: Subject Exclusion Criteria
 
21. Is a study site employee, staff, or close relative as defined.
 
 • PIs and Sub-Investigators • Staff who are supervised by the PI, Sub-Investigators • Member of the team conducting this clinical trial • Children, spouse, partners, siblings, and parents of site staff 	
Added definitions of study site employee, staff, or close relative

Page 33: Randomization Procedures
 
Within each of the 4 study drug lots and the placebo cohort, subjects will be randomized 2:1 to provide PD or PK specimens at visits specified in the Schedule of Assessments (Appendix A).
	
Page 38: Randomization Procedures
 
Within each of the 4 study drug dose/lots and the placebo cohort, subjects will be randomized 2:1 to provide PD or PK specimens at visits specified in the Schedule of Assessments (Appendix A).
	
Added study drug dose/lots

Page 34: Withdrawal or Discontinuation by Investigator
 
 • At the request of the Institutional Review Board (IRB)/Independent Ethics Committee (IEC), Food and Drug Administration (FDA), or Department of Defense (DOD). 	
Page 39: Withdrawal or Discontinuation by Investigator
 
 • At the request of the Institutional Review Board (IRB)/Independent Ethics Committee (IEC) or Food and Drug Administration (FDA) 	
Added clarification for reasons a subject may be removed

Page 39: Electrocardiogram
 
A 12-lead ECG will be performed at screening and reviewed by the study PI or a co-Investigator to assess the cardiac status of a subject for eligibility for enrollment. ECGs will be performed after the subject rests quietly
	
Page 44: Electrocardiogram
 
A 12-lead ECG will be performed at screening and Day 15 and reviewed by the study PI or a co-Investigator to assess the cardiac status of subjects for enrollment and for any significant changes at Day 15. ECGs will be
	
Added a 12-lead ECG at study visit 6, day 15

in a supine position for at least 10 minutes.	performed after the subject rests quietly for at least 10 minutes.	

Page 39: Drug Screen
 
A urine toxicology screen will be performed to detect for the presence of the following: cocaine (and metabolite), barbiturates, benzodiazepines, opiates, THC, methamphetamine/amphetamine, methadone and PCP. The results must be negative for eligibility into the study. A breathalyzer test will also be performed and results must be negative for eligibility into the study.
	
Page 44: Drug Screen
 
A urine toxicology screen will be performed to detect for the presence of the following: cocaine (and metabolite), barbiturates, benzodiazepines, opiates, THC, methamphetamine/amphetamine, methadone and PCP. The results must be negative for eligibility into the study. If a subject has a positive urine drug screen that the PI believes is caused by a currently prescribed medication (except for THC), the PI may enroll the subject if they meet all inclusion criteria, and none of the exclusion criteria. A breathalyzer test will also be performed and results must be negative for eligibility into the study.
	Added clarification on positive urine drug screens
Page 45: Visit 6/Day 15 (± 2 Day) Follow-up	
Page 50: Visit 6/Day 15 (± 2 Day) Follow-up
 
 Obtain 12-lead ECG 	Added a 12 lead ECG at study visit 6, day 15

Page 55: Reporting Procedures: Serious Adverse Events
 
ICON plc PVSS will send SAEs with the ICON Drug Safety Physician assessment of causality, expectedness, and any impact on the benefit-risk ratio of the IP to Ology Bio. The DOD will be notified of SAE by Ology Bio.
	
Page 59: Reporting Procedures: Serious Adverse Events
 
ICON plc PVSS will send SAEs with the ICON Drug Safety Physician assessment of causality, expectedness, and any impact on the benefit-risk ratio of the IP to Ology Bio. The DOD and the FDA will be notified of the SAEs as appropriate, by Ology Bio. HRPO and IRB will be informed of any safety issues as appropriate, per safety management plan by ICON and the PI.
	Added safety reporting and clarified notification responsibilities

Page 60-61: Analysis Populations
 
Pharmacodynamic (PD) Description: All Safety population subjects who have at least one non-missing evaluable PD result following dosing. They will be analyzed according to the treatment they actually received.
	
Page 65: Analysis Populations
 
Pharmacodynamic (PD) Description: All Safety population subjects who have sufficient evaluable PD result following dosing. They will be analyzed according to the treatment they actually received.
	Added subjects who have sufficient evaluable PD result

Page 61: Analysis Populations
 
Pharmacokinetic (PK) Description: All Safety Population subjects who have at least one non-missing evaluable PK result following dosing. They will be
	
Page 65: Analysis Populations
 
Pharmacokinetic (PK) Description: All Safety Population subjects who have sufficient evaluable PK result following dosing. They will be analyzed
	Added subjects who have sufficient evaluable PK result

analyzed according to the treatment they actually received.	according to the treatment they actually received.	
Page 73: Appendix A: Schedule of Assessments	Page 78: Appendix A: Schedule of Assessments Added 12-Lead ECG at Visit 6, D15 (±2D)	Added a 12 lead ECG at study visit 6, day 15
Page 74: Appendix A: Schedule of Assessments 13. Serum from subjects who give consent will be stored for future use on Days 0, 8, and 30.	Page 79: Appendix A: Schedule of Assessments 13. Serum from subjects who give consent will be stored for future use.	Removed the days for future use collection
Page 76-77: Appendix B	Page 81: Appendix B Vital signs: Fever, Tachycardia, Bradycardia, Hypertension (systolic), Hypertension (diastolic), Hypotension (systolic), respiratory rate	Added vital signs to toxicity table of clinical adverse events

## Statistical Analysis Plan (SAP)

### Revision History

Version	Date	Revisions
0.1	08-DEC-2022	Initial draft
0.2	18-JAN-2023	Second draft
1.0	09-FEB-2023	Final version
1.1	05-JUN-2024	
Updates to Statistical Analysis Plan following protocol amendment for inclusion of Cohort 4:
 

- Section 2 Study Objectives: Study objectives updated per protocol v4.0

- Section 3 Study Design:

o Inclusion/exclusion criteria updated per protocol v4.0

o General Study Design sub-section updated for Cohort 4

- Section 4 Types of Planned Analyses:

o Language updated regarding DSMB statistical analyses and interim analysis

- Section 5 Study Endpoints:

o Endpoints updated per protocol v4.0

- Section 6 Sample Size and Power:

o Detail added for sample size of Cohort 4

- Section 9 Statistical Methods:

o Language updated throughout for addition of Cohort 4 and its schedule of assessments as it pertains to statistical analysis (ie, study visits)

o Language updated in endpoint sub-sections to describe the updated endpoints per protocol v4.0

- Section 11 Appendix:

o Cohort 4 schedule of assessments added

1.2	13-AUG-2024	

- Sponsor feedback addressed from v1.1

- Section 9 Statistical Methods:

o Three cumulative incidence AE summaries across all cohorts added to Primary Endpoint 1a

1.3	09-MAY-2025	

- Section 8.3 Handling of Missing Data and Outliers: Language added to specify handling of laboratory values with non-numeric qualifiers (eg, inequalities)

- Section 9.10.1 Primary Endpoint 1a: Language added to specify that AE table summaries to include only events reported through subjects' final scheduled study visits

- Protocol reference updated to v5.0 06Jan2025

2.0	23-MAY-2025	

- Up-versioned to final version v2.0

## Statistical Analysis Plan (SAP)

### List of Abbreviations

Abbreviation	Explanation
ADA	Anti-Drug Antibody
AE	Adverse Event
ALT	Alanine aminotransferase
AST	Aspartate aminotransferase
AUC	Area Under the Curve
BLQ	Below Limit of Quantitation
BMI	Body Mass Index
BoNT	Botulinum Neurotoxin
C max	Maximum Plasma Titer/Concentration
CRF	Case Report Form
CRO	Contract Research Organization
CSR	Clinical Study Report
CV	Coefficient of Variation
DSMB	Data Safety Monitoring Board
ECG	Electrocardiogram
ECLA	Electrochemiluminescence Assay
ELISA	Enzyme-Linked Immunosorbent Assay
GCP	Good Clinical Practice
HBsAg	Hepatitis B Surface Antigen
HCG	Human Chorionic Gonadotropic Hormone
HCV	Hepatitis C Virus
HEENT	Head, Eyes, Ears, Nose and Throat
HIV	Human Immunodeficiency Virus
HR	Heart Rate
ICH	International Conference on Harmonization
IgE	Immunoglobulin E
IgG	Immunoglobulin G
IM	Intramuscular
INR	International normalized ratio
IP	Investigational Product
IRB	Institutional Review Board
ITT	Intention-To-Treat
Kg	Kilogram
mAb(s)	Monoclonal Antibody(ies)
MCH	Mean corpuscular hemoglobin
MCHC	Mean corpuscular hemoglobin concentration
MCV	Mean corpuscular volume
MedDRA®	Medical Dictionary for Regulatory Activities
MM	Medical Monitor
MNA	Battelle Mouse Neutralization Assay
MPV	Mean platelet volume
NAC	Neutralizing Antibody Concentration
PD	Pharmacodynamic
PE	Physical Examination
PI	Principal Investigator
PK	Pharmacokinetic
PP	Per-protocol
PT	Preferred Term
PTT	Partial Thromboplastin Time
Q1	First quartile
Q3	Third quartile
SAE	Serious Adverse Event
SAS®	Statistical Analysis Software
SD	Standard Deviation

## Statistical Analysis Plan (SAP)

---

SOC	System Organ Class
SOP	Standard Operating Procedure
TFLs	Tables, Figures, Listings
WFI	Water for injection

## Statistical Analysis Plan (SAP)

---

### 1 Introduction

The purpose of this Statistical Analysis Plan (SAP) is to provide detailed descriptions of the statistical methods, data derivations, and data displays for the study protocol G03-52-01-002, version 5.0, “A Phase 2, Randomized, Double-Blind, Placebo-Controlled Study to Evaluate the Safety, Tolerability, Pharmacodynamics, and Immunogenicity of G03-52-01 in Adult Subjects”, dated 06-JAN-2025. The table of contents and templates for the Tables, Figures, and Listings (TFLs) will be produced in a separate document.

Any deviations from this SAP will be described and justified in the Clinical Study Report (CSR).

The preparation of this SAP has been based on International Conference on Harmonisation (ICH) E9 and Good Clinical Practice (GCP) guidelines.

All data analyses and generation of TFLs will be performed using SAS® Version 9.4 or higher.

### 2 Study Objectives

#### 2.1 Primary Objectives

- To evaluate the safety and tolerability of single or repeat intramuscular (IM) administration of G03-52-01 in healthy adult subjects
- For Cohorts 1-3 (Cohorts 1-2 active IP and Cohort 3 is placebo)
  - Demonstrate target protective concentration (NAC) value  $> 0.02$  U/mL (BoNT/A) or  $> 0.03$  U/mL (BoNT/B) at Day 45 and Day 90
  - To evaluate lot-to-lot variability of two doses of G03-52-01 (Note: There will be no formal statistical analysis to support evaluation of lot-to-lot variability. In table summaries, the two lots within each of Cohorts 1 and 2 will be summarized and displayed separately to visually assess lot-to-lot variability.)
- For Cohort 4 (only active IP), demonstrate target protective concentration (NAC) value of BoNT/A and BoNT/B at 4 and 8 hours post-dose

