1. PROTOCOL SYNOPSIS

Name of Sponsor/Company: Resilience Government Services, Inc.	Individual Study Table Referring to Part of the Dossier: Volume: Page:	(For National Authority Use Only)
Name of Investigational Product: G03-52-01		
Name of Active Ingredient: NX01, NX02, NX11, XB10, XB18, and XB23		
Protocol Number: G03-52-01-002		
Title of Study: A Phase 2, Randomized, Double-Blinded, Placebo-Controlled Study to Evaluate the Safety, Tolerability, Pharmacodynamics, and Immunogenicity of G03-52-01 in Adult Subjects		
Study Center(s): Approximately 15 sites		
Phase of Development: Phase 2		
Study Duration: Approximately 8 months		
Subject Participation: Subject’s participation in Cohort 1-3 of the study is approximately 254 days (up to a 14-day screening, 1-hour inpatient stay and 240 days outpatient follow-up) Subject’s participation in Cohort 4 is approximately 134 days (up to a 14-day screening, 8-hour inpatient stay and 120 days outpatient follow-up)		
Objectives and Endpoints:		
Primary Objectives	Primary Endpoints	

 • To evaluate the safety and tolerability of single or repeat intramuscular (IM) administration of G03-52-01 in healthy adult subjects • Cohorts 1-3 
 ○ Demonstrate target protective concentration (NAC) value of BoNT/A and BoNT/B through Day 45 and Day 90 ○ To evaluate lot-to-lot variability of the two doses of G03-52-01 • For Cohort 4, demonstrate target protective concentration (NAC) value of BoNT/A and BoNT/B at 4 and 8 hours post dose 	
 • The occurrence of adverse events (AEs) and serious adverse events (SAEs) following administration of G03-52-01 to the final visit • The occurrence of changes from baseline in physical examination (PE), vital signs, and clinical safety laboratory values following administration of G03-52-01 to the final follow-up visit • For Cohorts 1-3, to evaluate target protective concentration (NAC) value > 0.02 U/mL (botulinum neurotoxin [BoNT]/A) or > 0.03 U/mL (BoNT/B) at Day 45 and Day 90 • For Cohort 4, to evaluate the proportion of subjects with target protective concentration (NAC) value > 0.02 U/mL (botulinum neurotoxin [BoNT]/A) or > 0.03 U/mL (BoNT/B) at 4 and 8 hours post dose 	

Secondary Objectives:
	
Secondary Endpoints:

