5. INVESTIGATIONAL PLAN

5.1. Study Design

This is a Phase 2, multicenter, randomized, double-blinded, placebo-controlled study to evaluate the safety, tolerability, pharmacodynamics (PD), and immunogenicity of a single dose (100 mg) and a repeat dose (50 mg and 100 mg) of G03-52-01 administered by IM injection(s) in adult subjects ([Appendix C](#)).

Approximately 625 subjects will be enrolled in this study to receive active product or placebo on Day 1 or Day 1 and Day 45, and will be randomized to the following concurrent cohorts:

- Cohort 1 (N=150, 75 lot #1, 75 lot #2): 50-mg dose
- Cohort 2 (N=150, 75 lot#1, 75 lot#2): 100-mg dose
- Cohort 3 (N=75): Placebo
- Cohort 4 (N=250): 100 mg dose or Placebo

The study will include up to 14-day screening period and an approximately 1-hour stay for Cohorts 1-3 and 8 hours stay for Cohort 4 in the clinic after dosing is complete for PK assessment and to ensure that no hypersensitivities or safety signals occur. Follow-up visits will occur at 24 hours and 72 hours post dose, and on Days 8, 15, 45, 49, 60, 90, 120, 150, 180, and 240 for Cohorts 1-3. For Cohort 4, follow-up visits will occur 24 hours, 72 hours, and on Days 8, 15, 30, 45, 90, and 120.

Safety Analysis

Safety labs will be drawn at pre-dose, 24 hours post dose, and on Days 15, 45 (before repeat-dose or placebo), 60, 120, and 240 for Cohort 1-3. Subjects in Cohort 4 will have safety labs drawn at screening and on Day 15, 45, and 120.

PD Analysis

PD samples will be collected for all subjects. Analysis will be completed by the Battelle Mouse Neutralization Assay (MNA) for Serotypes A and B.

Samples for subjects in Cohorts 1-3 will be tested at pre-dose, 24 hours post dose, and on Days 8, 15, 45 (before repeat-dose or placebo), 49, 90, and 120. The first 25 subjects randomized for each DP lot of 50 mg and 100 mg doses and placebo will be tested at all 8 timepoints. The remaining samples from the subjects who received either dose or lot of G03-52-01 (including placebo) will only be tested using MNA at pre-dose and Days 45, 90, and 120.

All subjects in Cohort 4 will have samples collected at pre-dose, 2 hours, 4 hours, 8 hours, 24 hours and on Days 30, 45, and 90. Samples will be analyzed for the first 30 subjects in Cohort 4, who receive active drug and complete the sample collection at 24 hours. See [Figure 2](#) and [Figure 3](#).

PK Analysis

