5.4.2. Randomization Procedures

Randomized treatment assignments will be generated by centralized randomization system. The system will be used each day that a subject, who has been screened and qualified at the site, returns for a study visit. Subjects will be randomized 2:2:1 to the following concurrent cohorts:

- Cohort 1: 50-mg dose of G03-52-01 on Day 1 and repeat 50-mg dose on Day 45 (N=150)
- Cohort 2: 100-mg dose of G03-52-01 on Day 1 and repeat 100-mg dose on Day 45 (N=150)
- Cohort 3: Placebo on Day 1 and placebo on Day 45 (N=75)

Within Cohorts 1 and 2, subjects will be randomized 1:1 to receive their study drug from Lots 1 or 2 of the drug. Within each of the 4 study drug dose/lots and the placebo cohort, subjects will be randomized 2:1 to provide PD or PK specimens at visits specified in the Schedule of Assessments ([Appendix A](#)).

Subjects in Cohort 4 will be randomized in a 4:1 to receive a single 100-mg dose of G03-52-01 or Placebo on Day 1 (N=250).

All individuals with access to study subjects or subject data will remain blinded until all data are entered and verified, and database is locked.

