### 3 Study Design

#### 3.1 General Study Design

This is a Phase 2, randomized, double-blind, placebo-controlled, multicenter trial to evaluate the safety, tolerability, pharmacokinetics (PK), pharmacodynamics (PD), and immunogenicity (ADA) of G03-52-01, administered by a 2-dose-regimen (Days 1 and 45) IM injections for Cohorts 1-3 and a 1-dose regimen (Day 1) for Cohort 4, in adult subjects.

In Cohorts 1-3, approximately 375 subjects between the ages of 18 and 65 years will be randomized in a 1:1:1:1:1 ratio to 5 parallel treatment groups, which constitute 3 cohorts with 150 subjects each for the two dosing cohorts (Cohort 1 50 mg G03-52-01 and Cohort 2 100 mg G03-52-01) and 75 subjects for the Cohort 3 Placebo group. Within each active dosing cohort, subjects will be randomized 1:1 to receive product from active drug Lot 1 or Lot 2. There is no lot within the Placebo cohort.

In Cohort 4, approximately 250 subjects between the ages of 18 and 65 years will be randomized in a 4:1 ratio to 2 treatment groups, which constitutes 1 cohort (Cohort 4) with 200 subjects randomized into the active group (Cohort 4 100 mg G03-52-01) and 50 subjects randomized into the Cohort 4 Placebo group.

Details regarding the planned assessments for each cohort can be found in the Study Treatments and Assessments section.

See Table 1 below for further details.

[figure not shown]

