### 4 Types of Planned Analyses

#### 4.1 Interim Analyses

An interim analysis is planned for the first 125 subjects in Cohorts 1-3 who complete through Day 120. An interim Clinical Study Report (CSR) is planned for the same 125 subjects across the three cohorts through Day 120. The data cut will take place when all 125 subjects have completed their 120 visits. The safety analysis will include all available safety data obtained from all subjects enrolled in the study up to the time of the fourth Data Safety Monitoring Board (DSMB) meeting.

The objectives of this interim analyses will be to compare safety between the 3 cohorts and to evaluate lot-to-lot variation in PK and PD parameters within the two active drug cohorts.

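### Lot-to-lot variability is a primary objective with randomised lots, but the SAP plans only side-by-side display, with no between-lot estimate or interval

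*SAP*

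**What the plan says.** The protocol synopsis lists among the primary objectives for Cohorts 1-3: "To evaluate lot-to-lot variability of the two doses of G03-52-01". Protocol 4.1 and SAP 2.1 repeat it. The design supports the comparison. Protocol 5.1 gives "Cohort 1 (N=150, 75 lot #1, 75 lot #2): 50-mg dose", with the same split for the 100 mg cohort, and SAP 3.1 describes subjects "randomized in a 1:1:1:1:1 ratio to 5 parallel treatment groups".

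On method, SAP 2.1 says "There will be no formal statistical analysis to support evaluation of lot-to-lot variability" and that "the two lots within each of Cohorts 1 and 2 will be summarized and displayed separately to visually assess lot-to-lot variability". SAP Table 2 repeats this note and gives the lot objective no contrast, interval or margin. Protocol 11.2 leaves the definition of the lot evaluation at the interim report to the SAP. SAP 4.1 names as an interim aim "to evaluate lot-to-lot variation in PK and PD parameters within the two active drug cohorts", again without a method.

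Some precision is planned within each lot. SAP 9.10.6 and 9.10.10, read with Table 2, give the geometric mean with its 95% CI, and the geometric CV with its 95% CI, by cohort and lot. For the primary protective-NAC endpoint, SAP 9.10.3 gives counts and percentages by lot and names no interval. SAP 9.1 offers 95% intervals only where relevant.

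The number of PD results per lot is not settled. Protocol 5.4.2 says that within each dose and lot "subjects will be randomized 2:1 to provide PD or PK specimens at visits specified in the Schedule of Assessments", whereas Protocol 5.1 says "PD samples will be collected for all subjects" and SAP 3.4 agrees with the latter.

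**The concern.** The randomisation makes the lot comparison a clean one, but the plan stops short of reporting its result. Two identical lots will always show somewhat different geometric means and protective rates. Without a ratio or difference and its interval, the study report can describe each lot but cannot say how large a lot difference the data leave open.

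The question matters to the product's case. Protocol 3.1.2 and 3.2 count variation between lots among the weaknesses of existing polyclonal antitoxins, and 3.2 lists consistent manufacture as an expected advantage of G03-52-01.

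**Working it through.** **The plan's own figures.** There is no power, margin or CV for the lot comparison to reproduce. The allocation adds up: 375/5 = 75 per lot per dose, and 150 + 150 + 75 + 250 = 625.

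**Subjects per lot per dose**
- 75, if PD is tested in all subjects at Days 45 and 90 (Protocol 5.1, SAP 3.4).
- 50, if the 2:1 split of Protocol 5.4.2 applies (75 × 2/3).
- 25, for full-profile PD and PK, hence AUC and Cmax. The interim report's 125 subjects also give 125/5 = 25 per group if spread evenly.

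**Assumption.** Between-subject CV of 30-60%, log-normal data. The documents give no value.

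**Geometric means.** With s = √ln(1 + CV²), the standard error (SE) of the log ratio is s√(2/n), and the 95% chance limits for identical lots are exp(±t × SE) with 2n − 2 degrees of freedom. Here s = 0.294 at CV 30% and 0.555 at CV 60%.

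| n per lot | t | SE, CV 30% | limits | SE, CV 60% | limits |
|---|---|---|---|---|---|
| 75 | 1.976 | 0.048 | 0.91-1.10 | 0.091 | 0.84-1.20 |
| 50 | 1.984 | 0.059 | 0.89-1.12 | 0.111 | 0.80-1.25 |
| 25 | 2.011 | 0.083 | 0.85-1.18 | 0.157 | 0.73-1.37 |

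Read upward, that is about 10-20%, 12-25% and 18-37%.

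**Protective-NAC rates.** The 95% chance difference for identical lots is 1.96√(2p(1 − p)/n).

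| n per lot | p = 50% | p = 95% |
|---|---|---|
| 75 | 16.0 points | 7.0 points |
| 50 | 19.6 points | 8.5 points |
| 25 | 27.7 points | 12.1 points |

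This is a normal approximation. It is rough at n = 25 and p = 95%, where only 25 × 0.05 = 1.25 failures per lot are expected.

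**Comparing two per-lot intervals by eye.** With equal standard errors e, two 95% intervals fail to overlap when the log means differ by more than 2 × 1.96e = 3.92e. The difference has standard error √2 × e, so the cut-off is z = 3.92/1.414 = 2.77, a two-sided level of 0.0056. Non-overlap is therefore about a 0.6% criterion, not 5%, and real differences would be passed over.

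**What a planned ratio would show.** At CV 40% with an observed ratio of 1.0, the 95% CI is 0.80-1.25 at 25 per lot, 0.86-1.17 at 50 and 0.88-1.13 at 75. Adjusting for dose across both cohorts gives about 0.90-1.11 (100 per lot) or 0.92-1.09 (150 per lot) for NAC. For AUC and Cmax the combined number is only 50 per lot.

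**The case against.** The best defence is that the trial is openly descriptive. Protocol 11.1 and SAP 6 rule out formal testing and power, the objective is to evaluate lot variability rather than demonstrate consistency, and the SAP does define how. That disposes of any demand for a test, an equivalence margin or more subjects, but not of an estimate with an interval. The SAP already uses intervals descriptively for geometric means.

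A reader might infer that lot differences cannot be told from chance at all, or that the objective has no answer. The documents do not support that for continuous data. From the planned per-lot intervals one can recover each log standard error as (ln upper − ln lower)/(2t), combine the two as the root of the sum of squares, and form the ratio's interval. Nor is any single chance range fixed by the documents, because it depends on the CV and on n. At CV 40%, identical lots would differ by more than a ratio of 1.30 in either direction only 1.6% of the time at 25 per lot and 0.07% at 50. Beyond 1.15, the figures are 20% at 25, 7% at 50 and 3% at 75. What remains is that a primary objective should not depend on back-calculation, and that the primary proportions carry no named interval.

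Two further objections stand in part:
- **Number of ratios.** NAC at two days (8), PD AUC and Cmax for both dosing periods (16) and PK AUC(0-t) and Cmax for six antibodies (48) make 72 ratios, before any pooled ones. With 95% intervals, about 72 × 0.05 = 3.6 would exclude 1 by chance. The set must be short.
- **Timing.** Protocol 3.1.3 reports that Cohorts 1-3 had completed their last visits, and the interim report has lot variation as an aim. An analysis added now may follow sight of lot results.

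**Conclusion.** The concern holds in a limited form. A primary objective, supported by randomisation, has no planned between-lot estimate or interval. The gap is clearest for the protective-NAC proportions in SAP 9.10.3. For NAC, PD and PK geometric means it is a gap in what is reported rather than in the information available.

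The chance limits rest on the assumed CV of 30-60%, log-normal data, assumed true rates of 50-95% and the number per lot. For the NAC endpoints at Days 45 and 90 in the final analysis, the relevant rows are 50 or 75 per lot. The 25-per-lot row applies to AUC, Cmax and the interim report. The protocol read here is dated 12 Apr 2024 while the SAP cites version 5.0, so the later version may settle which number applies. The missing contrast is in the SAP itself.

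**What to change.** - **SAP 9.10.3 and 9.10.6.** For each serotype at Days 45 and 90, add the Lot 2/Lot 1 geometric mean ratio of NAC and the Lot 2 minus Lot 1 difference in protective-NAC rate. Give each a 95% CI, in line with SAP 9.1, by dose and as one dose-adjusted estimate. A score-type interval suits rates near 100%.
- **PD and PK.** Name a short set in advance, for example AUC(0-t) and Cmax after Dose 1. By dose that is 8 PD ratios (2 parameters × 2 serotypes × 2 doses) and 24 PK ratios (2 × 6 antibodies × 2). Dose-adjusted only, it is 4 and 12.
- **Status.** Label all of these as descriptive, with no hypothesis test.
- **Below-limit values.** State how they enter the ratio. Under SAP 8.3, values below the limit become missing after a first measurable result but zero (0.001 in geometric means) before one. A low Day 45 value could therefore be handled differently in full-profile subjects and in those tested only at pre-dose and Days 45, 90 and 120.
- **Numbers.** Reconcile Protocol 5.1 with 5.4.2 and report the actual n per lot.
- **Timing.** Record the date of the addition and whether interim lot results had been seen.

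The cost is 24 NAC rows (2 serotypes × 2 days × 3 estimates × 2 measures) plus the short PD and PK set. It also needs a small code change: the planned PROC TTEST is one-sample and needs a lot comparison, and the dose-adjusted ratio needs a log-scale model with dose and lot. Intervals in the 25-per-lot subset will be wide, and the report should say so.
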